8.5.1.2. Criteria for Calculation and Reporting of Area Under the Concentration-time Curve

The minimum requirement for the calculation of AUC will be the inclusion of at least 3 consecutive concentrations above the lower limit of quantification. If there are only 3 consecutive concentrations, at least 1 should follow C_{max} .

 AUC_{0-inf} values where the percentage extrapolation is less than 30% will be reported. AUC_{0-inf} values where the percentage extrapolation is greater than 30% will be listed but excluded from descriptive statistics and statistical analysis.

8.5.1.3. Criteria for Handling Below the Limit of Quantification or Missing Concentrations for Pharmacokinetic Analysis

Plasma concentrations below the limit of quantification (BLQ) will be assigned a value of 0 before the first measurable concentration and thereafter BLQs will be treated as missing. The following rules apply with special situations defined below:

- If an entire concentration-time profile is BLQ, it will be excluded from PK analysis.
- Where 2 or more consecutive concentrations are BLQ at the end of a profile, the profile will be deemed to have terminated and any further quantifiable concentrations will be set to missing for the calculation of the PK parameters, unless they are considered to be a true characteristic of the profile of the drug.
- If a predose plasma concentration is missing, it may be set to 0 by default within Phoenix WinNonlin.

8.5.1.4. Treatment of Outliers in Pharmacokinetic Analysis

If a value is considered to be anomalous due to being inconsistent with the expected PK profile, it may be appropriate to exclude the value from the PK analysis. However, the exclusion of any data must have strong justification and will be documented in the CSR.

Any quantifiable predose concentration value will be considered anomalous and set to missing for the PK analysis.

8.5.2. Presentation of Pharmacokinetic Data

Individual concentrations deemed to be anomalous will be flagged in the listings and excluded from the summary statistics.

For PK concentration data the following rules will apply:

• Values that are BLQ will be set to 0 for the calculation of summary statistics.

- Arithmetic mean or median values that are BLQ will be presented as 0.
- If any BLQ results (treated as 0) are in a series of summarized data, geometric mean and CV of geometric mean will be reported as not calculated (NC).

For PK parameters the following rule will apply:

- For the calculation of summary statistics of PK parameters, all not reported (NR) and not calculated (NC) values in a data series will be set to missing.
- The AUC values will be set to NC if they have been calculated using fewer than 3 concentrations, and/or 3 concentrations if the last is C_{max}.
- Geometric mean and CV will not be calculated for t_{max} .

8.5.3. Pharmacokinetic Statistical Methodology

All PK concentrations and parameters will be listed.

Summary tables, mean (+ standard deviation [SD]) figures, overlaying individual figures, and individual figures by renal function and time postdose will be provided for plasma PK concentrations. All PK concentration figures will be produced on both linear and semi-logarithmic scales. The +SD bars will only be displayed on the linear scale.

Summary tables by renal function will be provided for all PK parameters, with the exception of diagnostic regression-related PK parameters. Summary statistics (n, Mean, SD, CV, minimum, median, maximum, geometric mean [Geom Mean] and geometric CV [Geom CV]) will be calculated for plasma LOXO-305 PK parameters. A Figure of individual PK parameters (AUC_{0-t}, AUC_{0-inf}, and C_{max}) and corresponding unbound PK parameters and corresponding geometric mean of PK parameters figures by renal function will be provided. Excluded subjects will be listed in the PK parameter tables, but will be excluded from the statistical analysis and summary statistics and noted as such in the tables.

The primary analysis planned for this study is to evaluate the PK of LOXO-305 after a single dose in subjects with renal impairment compared to subjects with normal renal function.

Paired t-tests will be performed to assess the differences in PK parameters (AUC_{0-t}, AUC_{0-inf}, and C_{max}) and corresponding unbound PK parameters between each renal impairment group versus the corresponding matched-control healthy group with respect to 1 to 1 matching. The analysis will be based on the natural log (ln)-transformed PK parameters. Geometric mean ratios and their corresponding 90% confidence intervals (CIs) will be calculated using the exponentiation of the mean difference and the CIs obtained for the difference in mean between each renal impairment group and the matching healthy control group.

Paired t-test Analysis:

```
proc ttest data = <data in> alpha=0.1;
by parcat1 paramn paramcd;
paired logaval&test.*logaval&ref.;
ods output statistics = <data out>;
ods output ttests = <data out>;
```

run;

In addition, an analysis of covariance (ANCOVA) will be performed on the ln-transformed AUC_{0-t}, AUC_{0-inf}, and C_{max}. The ANCOVA model will contain a categorical factor of population for subjects with varied-degree renal impairment (severe, moderate, and mild) and matched-control healthy subjects, a categorical covariate (sex), and continuous covariates (age and BMI). Ratios of least squares means (LSM) and 90% CIs will be calculated using the exponentiation of the difference between renal function cohort LSM from the ANCOVA analyses on the ln-transformed AUC_{0-t}, AUC_{0-inf}, and C_{max}. In addition, an ANCOVA will be performed on the ln-transformed AUC_{0-t}, AUC_{0-inf}, and C_{max}.

ANCOVA Analysis:

```
proc mixed data = <data in>;
by parcatl paramn paramcd;
class &renimp sex;
model laval = &renimp sex age bmi / alpha=0.1 cl outp=pred residual
ddfm=kr;
lsmeans &renimp / cl pdiff=control('1') alpha=0.1;
ods output lsmeans = <data out>;
ods output diffs = <data out>;
ods output covparms = <data out>;
run;
```

The relationship between LOXO-305 PK parameters (ie, C_{max} and AUC) and measures of renal function (such as eGFR and creatinine clearance) may be explored using a linear regression approach or other methods. The effect of covariates such as age, BMI, and sex may be investigated.

Additionally, a scatterplot of the ln-transformed PK parameters (AUC_{0-t}, AUC_{0-inf}, and C_{max}) and corresponding unbound PK parameters versus eGFR be produced. The linear regression will be included on the plot, along with two-sided 90% confidence bands for the linear regression line. The Spearman rank correlation coefficient will also be calculated..

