### **Statistical Methods**

#### Pharmacokinetics

The primary analysis planned for this study is to evaluate the PK of LOXO-305 after a single dose in subjects with renal impairment compared to subjects with normal renal function.

Paired t-tests will be performed to assess the differences in PK parameters ( $AUC_{0-t}$ ,  $AUC_{0-inf}$ , and  $C_{\max}$ ) between each renal impairment group versus the corresponding matched-control healthy group with respect to 1 to 1 matching. The analysis will be based on the natural log (ln)-transformed PK parameters. Geometric mean ratios and their corresponding 90% confidence intervals (CIs) will be calculated using the exponentiation of the mean difference and the CIs obtained for the difference in mean between each renal impairment group and the matched-control healthy group.

In addition, an analysis of covariance (ANCOVA) will be performed on the ln-transformed  $AUC_{0-t}$ ,  $AUC_{0-inf}$ , and  $C_{\max}$ . The ANCOVA model will contain a categorical factor of population for subjects with varied-degree renal impairment (severe, moderate, and mild) and matched-control healthy subjects, a categorical covariate (sex), and continuous covariates (age and BMI). Ratios of least squares means and 90% CIs will be calculated using the exponentiation of the difference between renal function cohort least squares means from the ANCOVA analyses on the ln-transformed  $AUC_{0-t}$ ,  $AUC_{0-inf}$ , and  $C_{\max}$ . In addition, an ANCOVA will be performed on the ln-transformed  $AUC_{0-t,u}$ ,  $AUC_{0-inf,u}$ , and  $C_{\max,u}$ .

The specific procedures will be documented in the Statistical Analysis Plan (SAP).

The relationship between LOXO-305 PK parameters (ie,  $C_{\max}$  and AUC) and measures of renal function (such as eGFR and creatinine clearance) may be explored using a linear regression approach or other methods, as indicated in the SAP. The effect of covariates such as age, BMI, and sex may be investigated.

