#### 8.4.2. Statistical Methodology

The primary analysis planned for this study is to evaluate the PK of LOXO-305 after a single dose in subjects with renal impairment compared to subjects with normal renal function.

Paired t-tests will be performed to assess the differences in PK parameters (AUC0-t, AUC0-inf, and Cmax) between each renal impairment group versus the corresponding matched-control healthy group with respect to 1 to 1 matching. The analysis will be based on the natural log (ln)-transformed PK parameters. Geometric mean ratios and their corresponding 90% confidence intervals (CIs) will be calculated using the exponentiation of the mean difference and the CIs obtained for the difference in mean between each renal impairment group and the matching healthy control group.

In addition, an analysis of covariance (ANCOVA) will be performed on the ln-transformed AUC0-t, AUC0-inf, and Cmax. The ANCOVA model will contain a categorical factor of population for subjects with varied-degree renal impairment (severe, moderate, and mild) and matched-control healthy subjects, a categorical covariate (sex), and continuous covariates (age and BMI). Ratios of least squares means and 90% CIs will be calculated using the exponentiation of the difference between renal function cohort least squares means from the ANCOVA analyses on the ln-transformed AUC0-t, AUC0-inf, and Cmax. In addition, an ANCOVA will be performed on the ln-transformed AUC0-t,u, AUC0-inf,u, and Cmax,u.

The relationship between LOXO-305 PK parameters (ie, Cmax and AUC) and measures of renal function (such as eGFR and creatinine clearance) may be explored using a linear regression approach or other methods. The effect of covariates such as age, BMI, and sex may be investigated.

The specific procedures will be documented in the SAP.

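### The second ANCOVA sentence in SAP 8.5.3 repeats the total-drug parameters where the protocol names the unbound ones, so the SAP text assigns no ANCOVA to unbound exposure

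*SAP*

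**What the plan says.** **SAP 8.5.3.** The ANCOVA paragraph first plans a model for log-transformed total AUC0-t, AUC0-inf and Cmax, with renal function group, sex, age and BMI as terms. It then describes the output: "Ratios of least squares means (LSM) and 90% CIs will be calculated using the exponentiation of the difference between renal function cohort LSM", again for the total-drug parameters. It ends: "In addition, an ANCOVA will be performed on the ln-transformed AUC_{0-t}, AUC_{0-inf}, and C_{max".

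**Protocol.** Section 8.4.2 has the same paragraph in the same order, but its closing sentence is "In addition, an ANCOVA will be performed on the ln-transformed AUC 0-t,u , AUC 0-inf,u , and C max,u". The Synopsis, under Statistical Methods, agrees: "In addition, an ANCOVA will be performed on the ln-transformed $AUC_{0-t,u}$ , $AUC_{0-inf,u}$ , and $C_{\max,u".

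**Unbound analyses that the SAP names.** In 8.5.3 the paired t-tests cover total drug "and corresponding unbound PK parameters between each renal impairment group versus the corresponding matched-control healthy group with respect to 1 to 1 matching". On summaries: "Summary tables by renal function will be provided for all PK parameters, with the exception of diagnostic regression-related PK parameters". Scatterplots are planned for the log-transformed total parameters "and corresponding unbound PK parameters versus eGFR be produced".

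**Precedence.** SAP Section 1 says that analyses generally follow the protocol unless modified by agreement, that the SAP supersedes the protocol's statistical considerations, and that substantial differences will be identified. SAP Section 10 reports no significant changes. Protocol 8.6 has the tables, figures and listings programmed from the final SAP.

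**The concern.** A sentence that opens as an addition and then lists the parameters already covered adds nothing. The protocol shows what was probably meant. As the SAP text stands, a programmer working from it has no written instruction to run the ANCOVA on unbound exposure.

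Unbound Cmax and AUC appear under Primary Endpoints in both documents (Protocol 2.2.1, SAP 3.1). In Protocol 8.4.2 the paired t-tests name total drug only, so the ANCOVA is the one formal group comparison that the protocol expressly plans for unbound exposure. The SAP adds the unbound parameters to the paired t-tests but, as read, drops them from the ANCOVA. From the text alone, a reader cannot tell a typing slip from an unannounced substitution of one method for the other.

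**Working it through.** No stated figure is in dispute, and the sample size was not derived from a power calculation. The check is therefore mainly a comparison of texts.

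**1. Sentence by sentence.**

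| Element | Protocol 8.4.2 and Synopsis | SAP 8.5.3 |
|---|---|---|
| Paired t-tests | total | total and unbound |
| First ANCOVA sentence | total | total |
| LSM ratio and 90% CI sentence | total | total |
| Second ANCOVA sentence | **unbound** | **total (repeated)** |

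Two rows differ. The paired t-test row is an addition in the SAP. The last row is the point at issue.

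**2. Is the unbound ANCOVA assigned elsewhere in the SAP?** Unbound parameters are defined in 3.1 and 8.5.1, and named in 8.5.3 for the paired t-tests, figures and eGFR scatterplots. No sentence links them to the ANCOVA.

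**3. Does the code settle it?** The PROC MIXED step runs by parameter code and contains no parameter list. It would run unchanged on unbound parameters, but it does not say whether they go in. It already requests least squares means, differences from control and limits at alpha = 0.1, so it would give the adjusted log differences and 90% limits for any parameter supplied.

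**4. Does the repeated total-drug ANCOVA stand in for the unbound one?** SAP 8.5.1 defines AUC0-inf,u as AUC0-inf × fu, so ln(AUC0-inf,u) = ln(AUC0-inf) + ln(fu), and likewise for the other two. On the same subjects, a linear model gives

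adjusted log ratio (unbound) = adjusted log ratio (total) + adjusted log ratio (fu).

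The two results coincide only if the adjusted fu ratio is 1. No ANCOVA of fu is planned, so the total-drug result does not supply the unbound one.

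**5. Does the unbound paired t-test stand in for it?** Partly. It compares the same groups, but by a different estimate. For severe versus normal, assume complete data, a distinct control for each subject and both sexes present. Paired df = pairs − 1. ANCOVA residual df = N − 5 (intercept, group, sex, age, BMI).

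| Completers | Paired df, t at 0.95 | ANCOVA df, t at 0.95 |
|---|---|---|
| 6 pairs (N = 12) | 6 − 1 = 5, 2.015 | 12 − 5 = 7, 1.895 |
| 8 pairs (N = 16) | 8 − 1 = 7, 1.895 | 16 − 5 = 11, 1.796 |

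This shows only that the analyses are distinct. Which interval is narrower also depends on the within-pair and residual variances, which the documents do not give. The handling of incomplete pairs differs too. If one member has no reportable AUC0-inf (R²-adj below 0.7, SAP 8.5.1.1; extrapolation above 30%, SAP 8.5.1.2), the paired test loses the pair, while the ANCOVA keeps the other subject.

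**6. Could the missing subscript be an artefact?** The SAP text shows lost or repeated runs elsewhere: a bracketed group list in Section 4 is cut short, an adverse event clause in Section 4 is repeated, and the QTcF sentence for the severe group in 8.6.4 appears twice. Against that, the unbound subscript survives in the abbreviations, 3.1 and 8.5.1, and it would have to vanish from all three parameters in one sentence. The text cannot decide between the two.

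**The case against.** The strongest reply is that the analysis was never withdrawn. The protocol specifies it twice. SAP Section 1 takes the protocol as the basis and promises to identify substantial differences, and none is identified. A statistician with both documents open would probably read the redundant sentence as meaning the unbound parameters. The code would handle them without change, and the TFL shells, which accompany the SAP and are not available here, may already list the table. The missing subscript may not exist on the original page at all.

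Most of this stands, and it limits the point to a wording inconsistency to be checked. It does not remove it: the SAP is the superseding document and the one programmed from, and silence in Section 10 is just what an unnoticed slip would leave.

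The documents do not support three stronger readings:

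- **That the sponsor dropped the adjusted unbound analysis, or replaced it with the paired test.** Nothing records such a decision, and the declared absence of changes points the other way.
- **That the sentence on LSM ratios and 90% confidence intervals is a second defect because it names total drug only.** The protocol's own sentence, "Ratios of least squares means and 90% CIs will be calculated using the exponentiation of the difference between renal function cohort least squares means", has the same scope, so the documents do not disagree there. The code already requests these quantities for any parameter it is given.
- **That the unadjusted unbound ratios would be biased by a stated amount.** That would need covariate slopes, within-pair gaps and variances, and the documents give none.

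**Conclusion.** The point holds as a minor inconsistency between protocol and SAP. As read, SAP 8.5.3 names total-drug parameters in both ANCOVA sentences, no other SAP sentence assigns an ANCOVA to unbound exposure, and Section 10 declares no change. A drafting slip or a reading artefact is likely, and confidence that the SAP page itself is wrong is only moderate until that page is seen.

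The size of the effect cannot be computed from the documents. It is bounded in kind: the total-drug analyses are untouched, and unbound exposure keeps its paired geometric mean ratios with 90% confidence intervals, its summaries and its eGFR plots. What would be missing is the covariate-adjusted, unpaired comparison of unbound exposure that the protocol planned.

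**What to change.** 1. Check the original page of SAP 8.5.3 and the TFL shells. If the page carries the unbound subscripts, nothing needs changing.
2. If it reads as above, replace the parameter list in the second ANCOVA sentence with AUC0-t,u, AUC0-inf,u and Cmax,u, run the existing PROC MIXED step on them, and confirm that the shells contain the matching table.
3. If the omission was intended, declare it in SAP Section 10 with the reason.

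The cost is three parameter names in one sentence and one more pass of code already written, or one sentence in Section 10. No new data are needed.

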8.6. Safety and Tolerability Assessments

8.6.1. Adverse Events

All AEs will be coded using the Medical Dictionary for Regulatory Activities (MedDRA) Version 23.0. All AEs will be assigned severity grade using Common Terminology Criteria for Adverse Events (CTCAE) Version 5.0.

A treatment-emergent adverse event (TEAE) will be defined as an AE that starts during or after LOXO-305 dosing, or starts prior to LOXO-305 dosing and increases in severity after LOXO-305 dosing.

A treatment-related TEAE will be defined as a TEAE with a relationship of related to the study treatment (LOXO-305), as determined by the investigator.

All AEs will be listed. In addition to the data recorded in the database, the listings will include derived onset time and duration. Onset time will be calculated from the time of dosing for TEAEs only.

The frequency of subjects with TEAEs and the number of TEAEs will be summarized for the following categories:

- TEAEs (overall, serious, leading to discontinuation, and leading to death) by renal function group
- TEAEs by severity and renal function group
- Treatment-related TEAEs (overall, serious, leading to discontinuation, and leading to death) by renal function group
- Treatment-related TEAEs by severity and renal function group

The frequency of subjects will be summarized separately for TEAEs and treatment-related TEAEs by the following:

- System organ class, preferred term, and renal function group
- Preferred term and renal function group

For the AE data the following rules will apply:

- For the derivation of TEAE status: If the start date/time of an AE is incomplete or missing, an AE will be assumed to be a TEAE, unless the incomplete start date/time or the end date/time indicates an AE started prior to dosing.
- For the derivation of treatment-related TEAE status: If the study treatment relationship for a TEAE is missing, a TEAE will be assumed to be a treatment-related TEAE.
- For the derivation of onset time: If the start date/time of an AE is missing, onset time will not be calculated. If the start date/time of an AE is incomplete, where possible, the minimum possible onset time will be calculated and presented in '≥DD:HH:MM' format (eg, if the date/time of dosing is 01MAY2019/08:00 and recorded start date/time of an AE is 03MAY2019, then the minimum possible onset time will be calculated by assuming the AE started at the first hour and minute of 03MAY2019
 [03MAY2019/00:00], thus will be presented as onset time ≥01:16:00 in the listing).
- For the derivation of duration: If the end date/time of an AE is missing, duration will not be calculated. If the start or end date/time of an AE is incomplete, where possible, the maximum possible duration will be calculated and presented in '≤DD:HH:MM' format (eg, if the start of an AE date/time is 01MAY2019/08:00 and its recorded end date/time is 03MAY2019, then the maximum possible duration will be calculated by assuming the AE ended at the last hour and minute of 03MAY2019 [03MAY2019/23:59], thus will be presented as duration ≤02:15:59 in the listing).

• For the calculation of summary statistics: If a subject experienced multiple TEAEs with the same preferred term for the same treatment, this will be counted as 1 TEAE for that treatment under the maximum severity recorded.

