Treatment-emergent AEs reported following LOXO-305 administration in healthy volunteers in the LOXO-BTK-20008 study (injection site pain, nasal congestion, flatulence, constipation, increased urinary frequency, facial rash, and sore right arm), were all Grade 1 in severity, and flatulence, constipation, and increased urinary frequency were considered to be related to LOXO-305. All 7 AEs were reported by 3 subjects and all events resolved within 1 to 8 days (preliminary data on file at the time of this protocol's development).

Adverse events reported following LOXO-305 administration in healthy volunteers in the LOXO-BTK-20016 study (petechiae [x4], back pain, nausea, constipation, bilateral leg cramps, facial acne, epigastric abdominal pain, and brain fog) were all Grade 1 in severity, and petechiae [x4], constipation, bilateral leg cramps, epigastric abdominal pain, and brain fog were considered to be related to LOXO-305. All 11 AEs were reported by 7 subjects and all events resolved within 1 to 11 days (preliminary data on file at the time of this protocol's development).

There have been no TEAEs reported following LOXO-305 administration in healthy volunteers and volunteers with varying degrees of hepatic impairment in the LOXO-BTK-20012 and LOXO-BTK-20010 studies to date (preliminary data on file at the time of this protocol's development).

Adverse events reported following LOXO-305 administration in healthy volunteers in the LOXO-BTK-20009 study (petechial rash and lightheadedness) were both Grade 1 in severity and petechial rash was considered to be related to LOXO-305. The 2 AEs were reported by 2 subjects and the events resolved within 1 to 6 days (preliminary data on file at the time of this protocol's development).

Adverse events reported following LOXO-305 administration in healthy volunteers in the LOXO-BTK-20011 study (headache [x4], dry mouth, rash [various locations; x9], pyuria, bacteriuria, intermittent left eye pain, lightheadedness, muscle twitch – right shoulder, diarrhea, slight tremor – left hand, constipation, and nausea) were all Grade 1 in severity. All 23 TEAEs were reported by 10 subjects and all but 8 TEAEs of rash had resolved within 1 to 9 days (preliminary data on file at the time of this protocol's development).

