6. STUDY TREATMENT AND RENAL FUNCTION GROUPS

The planned treatment administered for all subjects will be 200 mg LOXO-305.

The renal function group names and ordering to be used in the TFLs are presented in Table 2.

Renal Function Group	Abbreviation	Order in TFLs
Normal Renal Function	Normal	1
Mild Renal Impairment	Mild	2
Moderate Renal Impairment	Moderate	3
Severe Renal Impairment	Severe	4

All renal function groups described above are the planned groups. If the mild and moderate renal impairment groups are not enrolled, the subsequent order of the severe group will be amended. The TFLs will reflect the actual renal function groups dosed based upon their eGFR using the CKD-EPI equation.

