8.6.6. Safety and Tolerability Statistical Methodology

No inferential statistical analyses are planned.

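### As written, the SAP's one-per-preferred-term rule would turn the reported number of TEAEs into a count of subject-by-term pairs

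*SAP*

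**What the plan says.** SAP Section 8.6.1 describes two sets of AE summaries. The first covers TEAEs overall and by severity, and treatment-related TEAEs overall and by severity, all by renal function group. It is introduced with "The frequency of subjects with TEAEs and the number of TEAEs will be summarized for the following categories", so it carries both a subject count and an event count. The second, by system organ class and preferred term, is introduced with "The frequency of subjects will be summarized separately for TEAEs and treatment-related TEAEs by the following" and carries subjects only.

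The same section ends with data-handling rules. The last one is stated to apply whenever summary statistics are calculated, and it is triggered when one subject has repeat TEAEs of a single preferred term on one treatment. Its effect is given as "this will be counted as 1 TEAE for that treatment under the maximum severity recorded". It is the only counting rule for repeat events in either document. Protocol Section 8.5 says that AE incidence will be presented by severity and relationship, and gives no rule for counting events.

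The SAP also keeps the uncollapsed data: "All AEs will be listed".

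**The concern.** Counting a subject once per term at the worst grade is the usual convention for subject incidence. The SAP states it for summary statistics in general, however, and its unit is the TEAE rather than the subject. Applied to the event column, it replaces the number of events with the number of distinct subject-by-term pairs while the label stays the same.

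Three things would follow when a subject repeats a term:

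- The event total in the table would be smaller than the number of TEAEs in the listing.
- In the severity table, milder repeats would vanish from the event counts.
- Repeats of one term can differ in relationship to study drug, and the rule does not say which relationship the collapsed event keeps.

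Safety and tolerability is the secondary objective and is handled descriptively. Protocol Table 2 allows up to 8 subjects per impairment group, so one subject with several repeats would visibly change a group's event count. Two programmers could also read the section differently and produce different tables.

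**Working it through.** The plan states no figure to reproduce on this point, so the check is on the logic of the rule.

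**Inputs**

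- Event count promised for the overall, severity and treatment-related summaries: SAP 8.6.1.
- Collapsing rule, with no restriction to subject counts: SAP 8.6.1.
- One treatment per subject: SAP Section 6, "The planned treatment administered for all subjects will be 200 mg LOXO-305". The rule's same-treatment condition therefore excludes nothing.
- Event lists from earlier studies, for illustration: Protocol 1.4.1.

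**Formula**

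Let r(i,j) be the number of TEAEs of preferred term j in subject i.

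- Events: E = sum of r(i,j).
- Count under the rule as written: P = number of (i,j) pairs with r(i,j) ≥ 1.
- Shortfall: E − P = sum of (r(i,j) − 1) over those pairs. This is never negative, and it is zero exactly when no subject repeats a term.
- Subjects with any TEAE: the same under both counts.

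**Made-up example**

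Subject 1 has three separate headaches (grades 1, 1 and 2) and one nausea (grade 1). Subject 2 has one headache (grade 1).

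| | Each event counted | SAP rule as written |
|---|---|---|
| Number of TEAEs | 5 | 3 |
| Grade 1 | 4 | 2 |
| Grade 2 | 1 | 1 |
| Subjects with a TEAE | 2 | 2 |

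The shortfall is 5 − 3 = 2, and both lost events are grade 1.

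**Outer bounds on earlier event lists**

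The lower bound puts all repeats of a term in one subject; the upper bound has no subject repeating a term. Each reported word is treated as one preferred term, which is an assumption because coded terms are not given.

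- LOXO-BTK-20011 (QTc study): the Protocol says "All 23 TEAEs were reported by 10 subjects". The list is headache 4, rash 9 and ten single events: 4 + 9 + 10 = 23, which agrees. There are 12 distinct terms, so P lies between 23 − (4 − 1) − (9 − 1) = 12 and 23.
- LOXO-BTK-20016 (repaglinide study): petechiae 4 and seven single events: 4 + 7 = 11, which agrees with the stated total. There are 8 distinct terms, so P lies between 11 − (4 − 1) = 8 and 11.

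The stated numbers of affected subjects (10 and 7) do not narrow either range. The Protocol does not say how repeats were spread over subjects, so neither study can be placed within its range.

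**Relationship**

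In LOXO-BTK-20006, intermittent diarrhea was reported twice and Protocol 1.4.1 calls one instance related. Whether both occurred in one subject is not stated. If they did, the rule gives no answer on how the single collapsed event is classified.

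**The case against.** The strongest reply is that the sponsor means the rule for subject counts only, where it is standard, and that the table shells will show this. SAP Section 1 does refer the detailed table layouts to a separate shells document, which is not among the documents reviewed. That may well be the intention, but the SAP text does not say so.

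A second reply is that a stated convention is a definition and not an error. This is partly right: if the column were labelled as subject-by-term occurrences, nothing would be wrong. Section 8.6.1 labels it as the number of TEAEs.

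A third reply concerns consequence, and it stands. The two counts differ only if a subject repeats a term, in a single-dose study with confinement to Day 8. Every AE is listed by subject, so no information is lost, and for safety "No inferential statistical analyses are planned". All healthy-volunteer events whose grade is given in Protocol 1.4.1 were Grade 1, so those data contain no example of a lower grade being dropped.

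A reader might infer from the ranges above that the event count will be too low by up to 11/23 = 48% or 3/11 = 27%. The documents do not support that as a forecast:

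- LOXO-BTK-20011 tested a dose that Protocol 1.4 calls suprathreshold, and LOXO-BTK-20016 gave 200 mg daily for 11 consecutive days.
- Reaching 12 needs all nine rashes in one subject and all four headaches in one subject.
- In other studies at 200 mg the rule would change nothing: LOXO-BTK-20014 had three events with three different terms, LOXO-BTK-20009 had two different events in two subjects, and the hepatic impairment study LOXO-BTK-20012 had no TEAEs to date.
- LOXO-BTK-20007, with single 200 mg oral doses, did report some terms twice (loose stool; venipuncture-site tenderness; left antecubital bruising), again without saying whether the same subject was involved.

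Nor would it be right to infer that the safety evaluation rests on this table alone, because the listings stand beside it.

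**Conclusion.** The point holds as a conditional one. If the rule is applied as written, and if a subject repeats a preferred term, the reported number of TEAEs is a subject-by-term count that falls short of the listing, and lower-grade repeats drop out of the event counts by severity. Its size in this trial cannot be derived from the documents; it could be zero.

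The conclusion rests on the SAP text alone and could be softened by the unseen shells. The number of subjects with TEAEs does not change. Placing a subject at the maximum grade for a term is normal practice in subject tables. The listings and the PK analysis are untouched. This is a minor correction, worth making because the rule as stated contradicts the label of the quantity it governs.

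**What to change.** Limit the existing sentence in SAP 8.6.1 to the number of subjects: a subject with repeat TEAEs of one preferred term is counted once for that term, at maximum severity. Then add that, for the number of TEAEs, each distinct TEAE is counted once at its own severity. An episode entered on several lines because its grade changed counts as one event, at its highest grade; without that clause, counting every record could overcount.

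Alternatively, keep the rule and relabel the column as distinct subject/preferred-term occurrences. In that case, also state how relationship is assigned when repeats of one term differ.

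The cost is one SAP sentence and a minor programming check on how grade changes are recorded. No new data or design change is needed.
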